Safety data are available from the two Phase 2 studies (N = 575) which showed that the types and frequencies of AEs during upadacitinib treatment were consistent with subjects with moderately to severely active RA receiving immunomodulatory therapy. The incidences of AEs were numerically higher in the upadacitinib dose groups, with a trend toward higher rates with higher doses of upadacitinib. The most frequently reported AEs ( $\geq 5\%$ ) in the upadacitinib treated subjects were urinary tract infection, headache, upper respiratory tract infection, and nausea. There were 6 subjects (1.3% of total combined populations) with herpes zoster reactivation distributed across the upadacitinib dose groups, and 2 subjects (1.9%) in the placebo groups. In these two 12 week studies, a total of 2 subjects in the upadacitinib treatment groups reported malignancies. One subject reported non-melanoma skin cancers (NMSC) (basal cell and squamous cell carcinoma) and 1 subject was diagnosed with lung cancer after the final scheduled visit, and subsequently died 14 weeks after study completion. These events were reported by the Investigators as not possibly related to study drug. Elevations of liver function tests were sporadic with no clear dose-response relationship observed. As observed with other JAK inhibitors, treatment with upadacitinib resulted in an increase in lipids (low-density lipoprotein cholesterol [LDL-C] and high density lipoprotein cholesterol [HDL-C]). Among subjects with laboratory evidence of systemic inflammation (as evidenced by high-sensitivity C-reactive protein [hsCRP]  $>$  upper limit of normal [ULN]), treatment with lower doses of upadacitinib (3 mg BID and 6 mg BID) was associated with improvements in mean hemoglobin relative to placebo. At higher doses, there was a reduction in mean hemoglobin; however, the mean hemoglobin levels remained within normal range throughout the treatment period.

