#### **6.1.1.3 Adverse Events of Special Interest**

The following AEs of special interest will be monitored during the study (see detailed toxicity management in Section [6.1.7](#)):

- Serious infections;

- Opportunistic infections;
- Herpes zoster;
- Tuberculosis;
- Malignancy (all types);
- Gastrointestinal perforations;
- Adjudicated cardiovascular events (e.g., major adverse cardiovascular event [MACE]);
- Lipid profile changes;
- Anemia;
- Neutropenia;
- Lymphopenia;
- Increased serum creatinine and renal dysfunction;
- Hepatic events and increased hepatic transaminases;
- Elevated creatine phosphokinase (CPK).
- Embolic and thrombotic events (non-cardiac, non-CNS).

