##### **8.1.5.2.1 Treatment-Emergent Adverse Events (TEAE)**

AEs will be coded using MedDRA. A TEAE is defined as AE that began or worsened in severity after initiation of study drug.

AEs starting more than 30 days following the last dose of study drug will not be included in summaries of TEAEs. For subjects who continued into Period 2, AEs that are reported in Period 2 will be captured in the combined safety analysis of Period 1 and Period 2.

As a general safety summary, the number and percentage of subjects experiencing TEAEs will be summarized for each treatment group for the following AE categories:

- All AEs;
- All severe AEs;
- All reasonably possibly related AEs;
- All SAEs;
- Frequent AEs (reported in 2% of subjects or more in any treatment group);
- Frequent reasonably possibly related AEs (reported in 2% of subjects or more in any treatment group);
- Discontinuations due to AEs;
- Death.

Additional AEs may be considered for tabulation/summary based on recommendations from Clinical and Safety as deemed appropriate.

TEAEs will be summarized and presented by system organ classes (SOCs) and preferred terms (PTs) using MedDRA. The SOCs will be presented in alphabetical order, and the PTs will be presented in alphabetical order within each SOC.

TEAE will also be summarized by maximum severity and by maximum relationship.

The AEs of special interest (including but not limited to serious infection, opportunistic infection, herpes zoster, TB, gastrointestinal perforations, malignancies, adjudicated cardiovascular events (e.g., major adverse cardiovascular event [MACE]), lipid profile changes, anemia, neutropenia, lymphopenia, increased serum creatinine and renal dysfunction, hepatic events and increased hepatic transaminases, elevated CPK and non-cardiac, non-CNS embolic and thrombotic events) will be summarized. Event rate (per 100 patient years) for AEs of special interest will also be summarized for the combined safety analysis of Period 1 and Period 2.

---

All AEs leading to discontinuation of study drug will be presented in listing format. A listing by treatment group of TEAEs grouped by SOC and MedDRA preferred term with subject identification numbers will be generated.

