10.2.1.6 Adverse Events of Special Interest

The Adverse Events of Special Interest (AESI) categories will be summarized and presented by "as treated" treatment group using SOC and MedDRA PT. The AESI categories will be identified per Standard MedDRA Queries (SMQs)/Company MedDRA Queries (CMQs) in [Table 11](#) below. Adjudicated cardiovascular events will be summarized and presented by treatment group using the CAC adjudicated categories.

Table 11. AESI for Upadacitinib with SMQs/CMQs/PTs Searches

AESI	Type of MedDRA Query	Broad or Narrow Search	SMQ/CMQ Search Criteria
Serious Infections	CMQ		"Infections" – Subset for SAEs
Opportunistic Infection	CMQ		"Opportunistic Infection"
Possible Malignancy	SMQ	Narrow	"Malignancies"
Malignancy	SMQ		"Malignant tumours"
Non-Melanoma Skin Cancer (NMSC)	SMQ	Narrow	Skin Malignant tumours (Narrow SMQ) removing Melanoma CMQ
Malignancy excluding NMSC			"Malignant tumours" Narrow SMQ removing NMSC output
Lymphoma	SMQ		"Malignant Lymphomas"
Hepatic Disorder	SMQ	Narrow	"Drug Related Hepatic Disorders"
Gastrointestinal Perforations	SMQ	Narrow	"Gastrointestinal Perforation"
Anemia	CMQ		"Non-Hemolytic and Non-Aplastic Anemias"
Neutropenia	CMQ		"Hematological Toxicity – Neutropenia"
Lymphopenia	CMQ		"Hematological Toxicity – Lymphopenia (Veliparib Product Specific)"
Herpes Zoster	CMQ		"Herpes Zoster"
Creatine Phosphokinase (CPK) Elevation	PT		Search only for the PT of "Blood creatine phosphokinase increased"
Renal Dysfunction	SMQ	Narrow	"Acute Renal, Failure"
Tuberculosis	CMQ		"Tuberculosis"

Table 11. AESI for Upadacitinib with SMQs/CMQs/PTs Searches (Continued)

AESI	Type of MedDRA Query	Broad or Narrow Search	SMQ/CMQ Search Criteria
Adjudicated Cardiovascular Events	Output from CAC		
MACE*			
Undetermined/Unknown Cause of Death			
Other Cardiovascular events			
Venous Thromboembolic Events**			
Other Venous Thrombosis			
Arterial Thromboembolic Events (non-cardiac, non-neurologic)			

* MACE; Major Adverse Cardiovascular Events, defined as cardiovascular death, non-fatal myocardial infarction and non-fatal stroke.

** Venous thromboembolic events (VTE) include deep vein thrombosis (DVT) and pulmonary embolism (PE).

Additional AEs may be considered for tabulation/summary based on recommendations from Clinical and Safety as deemed appropriate.

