10.2.2.1 Overview of Adverse Events Rates per 100 Patient-Years of Study Drug Exposure

An overview of AEs per 100 patient-years of study exposure will be presented for upadacitinib 15 mg QD for the following AE categories.

- All TEAEs
- Treatment-emergent serious adverse events (SAEs)
- Treatment-emergent severe adverse events
- TEAEs reasonably possibly related to study drug
- TEAEs of special interest
- TEAEs leading to discontinuation of study drug
- TEAE leading to death

Additional AEs may be considered for tabulation/summary based on recommendations from Clinical and Safety as deemed appropriate.

10.2.2.2 Adverse Events Rates per 100 Patient-Years of Study Drug Exposure by SOC and PT

For upadacitinib 15 mg QD treatment group, the TEAE rate per 100 patient-years of exposure as outlined in Section 10.2.2 will be calculated overall, for each SOC and each PT, for each of the following events:

- All TEAEs
- Treatment-emergent serious adverse events (SAEs)
- Treatment-emergent severe adverse events
- TEAEs reasonably possibly related to study drug

- TEAEs leading to discontinuation of study drug
- TEAE leading to death

**10.2.2.3 Adverse Events of Special Interest Rates per
100 Patient-Years of Study Drug Exposure**

The Adverse Events of Special Interest (AESI) rate per 100 patient-years of exposure as outlined in Section 10.2.2 will be calculated overall, for each SOC and each PT, for each of the AESI listed in Section 10.2.1.6.

**10.2.2.4 Listing of Serious Adverse Events (Including Deaths) and
Adverse Events Leading to Study Drug Discontinuation**

All serious adverse events (SAEs), deaths, and adverse events leading to discontinuation of study drug will be listed.

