10.3.2.3 Assessment of Potentially Clinically Significant Laboratory Variables

The criteria for potentially clinically significant laboratory values will be determined by OMERACT criteria of Grade 3 or 4. For creatine phosphokinase and creatinine, NCI CTC criteria will be used.

The number and percentage of subjects meeting the criteria for potentially clinically significant laboratory values will be summarized by "as treated" treatment group. Only subjects with worsening in grade compared to baseline grade will be captured.

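### Lipid profile changes are a protocol AESI with a required event rate, but SAP Table 11 has no lipid row and the laboratory grading has no lipid criteria, so neither a lipid AESI summary nor a count of subjects crossing a lipid limit follows

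*SAP*

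**What the plan says.** **Protocol.** Section 6.1.1.3 has fifteen AESI bullets, one of them "Lipid profile changes". Section 8.1.5.2.1 lists the AESIs that will be summarized and includes "lipid profile changes, anemia, neutropenia, lymphopenia, increased serum creatinine and renal dysfunction, hepatic events and increased hepatic transaminases". It then adds: "Event rate (per 100 patient years) for AEs of special interest will also be summarized for the combined safety analysis" of the two periods. The list of changes in Appendix P shows that the lipid item entered this summary list with the current amendment, so naming it was deliberate.

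**SAP, adverse events.** Section 10.2.1.6 states: "The AESI categories will be identified per Standard MedDRA Queries (SMQs)/Company MedDRA Queries (CMQs) in" Table 11. Section 10.2.1.1 has an overview line for TEAEs of special interest, with a treatment difference and 95% CI. Section 10.2.2.1 has the matching long-term line. Section 10.2.2.3 calculates AESI rates "for each of the AESI listed in Section 10.2.1.6".

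**SAP, laboratory data.** Section 10.3.2.3 states: "The criteria for potentially clinically significant laboratory values will be determined by OMERACT criteria of Grade 3 or 4", with NCI CTC grades for CPK and creatinine. The shift tables in 10.3.2.2 and the long-term counts and listing in 10.3.3.2 rest on the same grades, which are set out in Appendix A. Section 10.3.2.1 plans mean change by visit and arm with an ANOVA between arms. It plans a similar analysis of percent change for LDL-C, HDL-C, triglycerides, total cholesterol and two lipid ratios. Section 10.3.3.1 repeats these summaries long term without a test.

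**The concern.** A lipid effect of this drug was already seen. In the Phase 2 summary the protocol reports that "treatment with upadacitinib resulted in an increase in lipids", naming LDL-C and HDL-C. Period 1 is the study's only randomized, placebo-controlled comparison of that effect, because every subject in Period 2 receives upadacitinib.

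For an expected effect, a safety reader wants to know how many subjects in each arm had a lipid event, at what rate over the whole study, and how many moved beyond a laboratory limit. The protocol promises the AESI summary and the rate. The SAP is the document that will be programmed, and it defines no lipid category for either. If nothing changes, the study report will show an AESI total that leaves out a protocol-defined category. Any later grouping of lipid terms would be chosen without pre-specification, possibly after treatment is unblinded.

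**Working it through.** No formula or stated figure is at issue, so the check sets the texts side by side.

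**Step 1. Protocol 6.1.1.3 against SAP Table 11.** Table 11 has 16 MedDRA-search rows plus the adjudicated cardiovascular outputs.

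| Protocol AESI | SAP Table 11 |
|---|---|
| Serious infections | Serious Infections |
| Opportunistic infections | Opportunistic Infection |
| Herpes zoster | Herpes Zoster |
| Tuberculosis | Tuberculosis |
| Malignancy | Five rows, including NMSC and lymphoma |
| Gastrointestinal perforations | Gastrointestinal Perforations |
| Adjudicated cardiovascular events | Adjudicated output |
| **Lipid profile changes** | **None** |
| Anemia | Anemia |
| Neutropenia | Neutropenia |
| Lymphopenia | Lymphopenia |
| Increased creatinine and renal dysfunction | Renal Dysfunction |
| Hepatic events and transaminases | Hepatic Disorder |
| Elevated CPK | CPK Elevation |
| Embolic and thrombotic events | Adjudicated venous and arterial outputs |

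15 categories − 14 with a counterpart = 1 without.

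**Step 2. What depends on Table 11.** Three kinds of output do: the AESI summary (10.2.1.6), the overview lines (10.2.1.1 with its treatment difference, and 10.2.2.1), and the AESI rates (10.2.2.3). None has a lipid definition to work from.

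**Step 3. Do the laboratory tables recover it?** Appendix A has haematology rows K1 to K5 and chemistry rows numbered L1 to L16. None covers total cholesterol, LDL-C, HDL-C or triglycerides, and the copy in protocol Appendix N has none either. No row L4 appears in either copy as supplied; I assume it is not a lipid row. Without a grade, these four analytes cannot enter the grade shift tables, the Grade 3 or 4 counts or the Grade 3 or 4 listing.

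**Step 4. What the SAP does still produce on lipids.**
- Mean change and percent change by visit and group, with a between-arm ANOVA in Period 1.
- Number and percentage of subjects by SOC and preferred term for every TEAE, by arm (10.2.1.2).
- A rate per 100 patient-years for each preferred term (10.2.2.2).
- A listing of subjects with TEAEs (10.1).

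**Step 5. Can the missing category be rebuilt from those outputs?** The rate can, once the terms are fixed. SAP 10.2.2 counts events, not subjects, over a common exposure T. For lipid terms j with e_j events, the category rate is 100 × Σe_j / T = Σ(100 × e_j / T), the sum of the preferred-term rates. What is missing is the pre-specified list of terms. The subject count cannot be rebuilt this way. A subject with two lipid terms is counted under both, so preferred-term percentages do not add up to the percentage with any lipid event.

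**Step 6. Are reported adverse events a full record of lipid rises?** No. Under protocol 6.1.1.1 a laboratory abnormality is an adverse event only if it leads to discontinuation, needs therapeutic intervention, or is judged an adverse event by the investigator.

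**The case against.** The strongest reply is that lipids are handled on purpose as laboratory data. The category describes a laboratory change, and SAP 10.3.2.1 singles out four lipid measures and two ratios for a percent-change analysis compared between arms. That analysis is real and useful. It does not explain the omission, because haemoglobin is in the same percent-change list and anemia still has a Table 11 row. Neutropenia, lymphopenia and CPK elevation are also laboratory findings with rows. Nor does the SAP say that laboratory data stand in for the lipid AESI.

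Four parts of the reply do stand.

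- A reader might infer that no subject-level lipid result will exist. The documents do not support that: lipid abnormalities reported as TEAEs are counted by subject and arm, given preferred-term rates, and listed.
- A reader might take Table 11 as exhaustive. SAP 10.2.1.6 allows further adverse events to be added on clinical and safety advice. That is discretionary and defines no lipid category, whereas the protocol's commitment to summarize is not optional.
- A new MedDRA row would draw on the same reported adverse events, so by itself it would not recover unreported lipid rises.
- Protocol 8.1.5.3 asks for shift tables by grade, and SAP 10.3.2.2 says they are made as deemed appropriate. No text promises a count of subjects moving from normal to high lipids. The shift table proposed here is a recommendation, not the repair of a broken promise.

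A reader might also extend the point to creatinine, because the renal row uses a narrow acute renal failure search. The documents do not support that. Creatinine has NCI CTC grades and enters the shift and clinically significant tables. Whether the renal query already includes an increased-creatinine term depends on MedDRA content that is not in the documents.

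**Conclusion.** The mismatch between protocol and SAP is real and limited. One of fifteen protocol AESI categories has no definition in the SAP. It therefore gets no category count and no pre-specified rate, and it is missing from the overall AESI line and its treatment difference. Separately, four lipid analytes have no criterion by which a subject could be counted as crossing a laboratory limit.

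The effect on the reported AESI numbers cannot be sized, because the documents give no expected count of lipid events. Efficacy inference is untouched; these are safety summaries. The point still deserves correction, because the effect is one the sponsor already observed and a group mean does not show how many subjects went out of range.

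The conclusion assumes that Table 11 is programmed as printed, that the discretionary sentence is not used to add lipids, and that the unseen row L4 is not a lipid criterion.

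**What to change.** 1. Add a Lipid Profile Changes row to SAP Table 11 with a pre-specified MedDRA search, so that it carries through to 10.2.1.1, 10.2.1.6, 10.2.2.1 and 10.2.2.3. Alternatively, state in 10.2.1.6 that this AESI is assessed through pre-specified laboratory categories, and reconcile that with the summary and event rate required by protocol 8.1.5.2.1.
2. Under either option, add shift tables to SAP 10.3.2.2 for total cholesterol, LDL-C, HDL-C and triglycerides by central-laboratory low, normal and high range. A MedDRA row reaches only the rises that were reported as adverse events.

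The cost is one table row, or a short statement with a protocol reconciliation, plus one set of shift tables on data already collected. Study conduct does not change. With the added row, the overall AESI count may come out slightly higher.

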## **6.1                   Medical Complaints**

The Investigator will monitor each subject for clinical and laboratory evidence of AEs on a routine basis throughout the study. The Investigator will assess and record any AE in detail including the date of onset, event diagnosis (if known) or sign/symptom, severity, time course (end date, ongoing, intermittent), relationship of the AE to study drug, and any action(s) taken. For SAEs considered as having "no reasonable possibility" of being associated with study drug, the Investigator will provide other cause(s) of the event. For AEs to be considered intermittent, the events must be of similar nature and severity. AEs, whether in response to a query, observed by site personnel, or reported spontaneously by the subject will be recorded.

All AEs will be followed to a satisfactory conclusion.

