**Table 8. Specific Toxicity Management Guidelines for Abnormal Laboratory Values (Continued)**

Laboratory Parameter	Toxicity Management Guideline
AST or ALT (continued)	
 
For subjects with HBc Ab+ (irrespective of HBs Ab status) and negative HBV DNA at screening who manifest an ALT > 5 × ULN OR ALT/AST > 3 × ULN and either a total bilirubin > 2 × ULN or INR > 1.5 OR ALT/AST > 3 × ULN along with clinical signs of possible hepatitis, HBV DNA by PCR testing should be performed within 1 week. A positive result for HBV DNA PCR testing in these subjects will require immediate interruption of study drug and a hepatologist consultation should occur within 1 week for recommendation regarding subsequent treatment.
 
 
For any confirmed ALT or AST elevations > 3 ULN, complete supplemental hepatic eCRF.

Serum Creatinine	
 
If serum creatinine is > 1.5 × baseline value and > ULN, repeat the test for serum creatinine (with subject in an euvolemic state) to confirm the results. If the results of the repeat testing still meet this criterion, then interrupt study drug and re-start study drug once serum creatinine returns to ≤ 1.5 × baseline value and ≤ ULN.
 
If confirmed serum creatinine ≥ 2 mg/dL, interrupt study drug and re-start study drug once serum creatinine returns to normal reference range or its baseline value.
 
 
For the above serum creatinine elevation scenarios, complete supplemental renal eCRF.

Creatine Phosphokinase	
 
For confirmed CPK value ≥ 4 × ULN, and there are no symptoms suggestive of myositis or rhabdomyolysis, the subjects may continue study drug at the investigator's discretion.
 
If CPK ≥ 4 × ULN accompanied by symptoms suggestive of myositis or rhabdomyolysis, interrupt study drug and contact the AbbVie TA MD.
 
 
For the above CPK elevation scenarios, complete supplemental CPK eCRF.

For allowed study drug interruption, the following rules apply:

### Period 1

- Allow study drug interruption up to 7 consecutive days for AEs and emergency surgery. Elective surgery will not be allowed during this 12 week period.

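### SAP Table 11 names no creatinine term for the protocol's combined creatinine and renal AESI, so such adverse events can fall outside the AESI counts, difference and rate

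*SAP*

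**What the plan says.** Protocol 6.1.1.3 lists among the AESIs "Increased serum creatinine and renal dysfunction" and, separately, "Elevated creatine phosphokinase (CPK"). Protocol 8.1.5.2.1 repeats both in the list of AESIs to be summarised ("increased serum creatinine and renal dysfunction, hepatic events and increased hepatic transaminases, elevated CPK") and adds an event rate per 100 patient-years for AESIs over Periods 1 and 2 combined.

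SAP 10.2.1.6 identifies the AESI categories through Table 11. Its Renal Dysfunction row is a narrow SMQ search, "Acute Renal, Failure". No other row concerns the kidney, and no creatinine term appears. Its CPK Elevation row reads "Search only for the PT of 'Blood creatine phosphokinase increased".

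Table 11 feeds three outputs: the AESI summaries in SAP 10.2.1.6, the Period 1 AESI treatment difference with a 95% CI in 10.2.1.1, and the long-term AESI rates in 10.2.2.3, which refer back to the list in 10.2.1.6.

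**The concern.** The protocol's renal AESI has two parts, and Table 11 shows how only one of them is found, through a query for acute failure. The SAP does not say that the creatinine part is to be reported elsewhere. A reader of the AESI table would take the Renal Dysfunction row to be the protocol AESI when it may be a subset of it.

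At stake are the outputs reserved for AESIs. Within the SAP's adverse event analyses, only AESIs receive a between-arm difference with a confidence interval. An event that the search misses loses that comparison. It also drops out of the combined figure for the risk that the protocol chose to monitor.

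**Working it through.** No figure in the plan can be reproduced here, because the documents give no event counts or expected rates for renal or creatinine events. The check is a comparison of definitions.

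**Protocol AESI against SAP search**

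| Protocol AESI (6.1.1.3, 8.1.5.2.1) | Table 11 search | Match on the face of the documents |
|---|---|---|
| Renal dysfunction | Narrow acute renal failure SMQ | Acute events covered; non-acute not shown |
| Increased serum creatinine | None named | Not shown |
| Elevated CPK | One preferred term for increased blood CPK | Yes |

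**Would such events arise as adverse events?** Protocol 6.1.1.1 makes a laboratory abnormality an adverse event if it leads to discontinuation from the study, needs therapeutic intervention, or is judged an adverse event by the investigator. Protocol 6.1 has the investigator record the "event diagnosis (if known) or sign/symptom". A creatinine rise without a diagnosis can therefore be recorded as just that.

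**Do the laboratory tables give the same information?** Only in part. SAP 10.3.2.3 counts Grade 3 or 4 values. Under the creatinine grading in SAP Appendix A, more than 1.5 and up to 3.0 times baseline is Grade 2. Protocol Table 8 calls for interruption of study drug at a confirmed value above 1.5 times baseline and above the upper limit of normal. A case that meets that rule can thus be Grade 2 and outside the count, although the shift tables in 10.3.2.2 would include it. None of these tables shows which values were adverse events.

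**Scale of one missed event.** This is not an estimate of the undercount.

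- Inputs: 161 subjects per arm; 64 weeks of upadacitinib for the upadacitinib arm (12 + 52) and 52 weeks for placebo subjects who switch; 365.25/7 = 52.18 weeks per year.
- No loss at all: 161 × (64 + 52) = 18,676 weeks, and 18,676 / 52.18 = 358 patient-years. One event is 100 / 358 = 0.28 per 100 patient-years.
- Assuming that 10% of the placebo arm is lost before Week 12 (the planned dropout rate in Protocol 8.2, applied here to that arm only): 161 × 64 + 161 × 0.9 × 52 = 10,304 + 7,535 = 17,839 weeks, or 342 patient-years. One event is 100 / 342 = 0.29.
- Later attrition lowers exposure and raises the per-event figure.
- Period 1: one subject missed in an arm of 161 moves that arm's AESI percentage by 1 / 161 = 0.6 percentage points.

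**The case against.** The strongest reply is that little is lost. SAP 10.2.1.2 tabulates all, serious, severe and related events, and those leading to discontinuation, by system organ class and preferred term for each arm. SAP 10.2.2.2 gives rates per 100 patient-years by preferred term, and 10.2.2.4 lists serious events and those leading to discontinuation. A creatinine preferred term would have its own line and its own rate. Creatinine values are graded, with shift tables and Grade 3 or 4 listings. The SAP also seems to handle other laboratory-type AESIs this way: lipid changes have no Table 11 row but are analysed as laboratory data, and transaminases have dedicated analyses in 10.3.2.4. Finally, the narrow query may already contain a creatinine term.

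Much of this stands, and it limits the point to the AESI outputs. What it does not supply is the AESI difference with its interval, the combined AESI figure, or a statement that creatinine is meant to be covered by laboratory data alone. The allowance for additional adverse event tabulations is discretionary.

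A reader might go further and infer that the CPK row has the same fault, because a rise recorded as myositis or rhabdomyolysis would escape a single laboratory term. The documents do not support calling that a mismatch. The protocol AESI is elevated CPK, and the search matches it. Muscle injury appears only in the toxicity rule of Protocol Table 8, for CPK rises "accompanied by symptoms suggestive of myositis or rhabdomyolysis". Muscle-injury terms would extend the AESI, not correct its search. A reader might also infer that every creatinine adverse event is lost. That depends on the contents of the query, which are not given.

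**Conclusion.** The point holds for the renal AESI and is minor. The protocol names increased serum creatinine as part of an AESI for which a rate is promised, and the SAP does not show how such events enter the AESI analyses. Events recorded as increased creatinine, or as non-acute renal dysfunction, can be omitted from the counts, the Period 1 difference and the long-term rate.

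The supported wording is that they can be omitted, not that they will be. The conclusion assumes that the narrow query does not already include the relevant terms. The number of events affected is unknown, so the undercount cannot be sized; the per-event figures above only give the scale. Overall safety reporting remains largely intact through the preferred-term tables, the listings and the laboratory summaries.

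**What to change.** In SAP Table 11, keep the existing renal row unchanged so that it stays comparable with other studies. Add a prespecified row for increased serum creatinine, identified by the creatinine-increased preferred term. Show the two rows separately and combined, with the combined row labelled as the protocol AESI and each subject counted once in its percentages. State whether the narrow query is meant to cover non-acute renal dysfunction and, if it does not, name the terms that will. Apply the definitions in SAP 10.2.1.1, 10.2.1.6 and 10.2.2.3. If the sponsor intends laboratory data alone to cover the creatinine part, the SAP should say so and give the reason.

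The cost is one change to a search definition before database lock, using coded data already held. AESI counts may rise slightly, and comparisons with studies that used the narrower search need a footnote. A supplementary muscle-injury row is an optional extension and is not needed to resolve this point.
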